9.2.2 Study time frame

We will use CPRD GOLD and Aurum EHR data from January 1, 2013 through latest available data (currently March 2019).

- Patient identification period: The patient identification period will be restricted to January 1, 2013 through latest available data as shown in the figure above.
- Cohort entry: CAT diagnosis, hospitalization or emergency department admission or primary care visit with an incident VTE event.
- Index date: The date of first rivaroxaban (or any DOAC) or LMWH use according to registered prescription 7-30 days after CAT event (new-user design).
- Pre-index eligibility period: Patients will be required to have at least 12-months of EHR registration prior to the CAT event.
- Post-index eligibility period: There will be no minimum post-index eligibility requirement for patient identification.
- Follow-up period: There will be a minimum of 3 months and maximum 12-months follow-up period. Patients will be followed from the first recording of AC use (7-30 days after CAT event) until the end of eligibility.

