9.3.2 Outcomes definition

The study outcomes will be defined based on Read codes and ICD-9/10-CM diagnosis and procedure codes or laboratory, vital sign and other patient observation results.

Algorithms for the definition of recurrent VTE and of the bleeding events have previously been developed and refined using all information available in CPRD, HES and Office of National Statistics ONS [4, 8].

A random sample of identified potential VTE recurrences and significant bleeding events will be manually reviewed by utilizing patient summaries/profiles including HES APC, HES Outpatient, ONS death registration data (DRD) and PCP recorded symptoms, signs, laboratory tests, diagnostic and therapeutic procedures, medication use, discharge diagnoses, and cause of death to confirm the that outcomes have been appropriately identified.

Primary outcomes

- The risk of recurrent VTE at 3-months
- Composite of any major bleeding or clinically-relevant non-major bleeding-related hospitalization (per the ISTH criteria [9, 10] for identification of bleeding-associated hospitalizations) at 3-months
- All-cause mortality at 3-months

Secondary outcomes

- Recurrent VTE at 6- and 12-months post-index VTE

- Composite of any major or clinically-relevant nonmajor bleeding-related hospitalization at 6- and 12-months post-index VTE, including:
 - Intracranial hemorrhage (ICH)
 - Critical organ bleeding (e.g., intracranial, intraspinal, intraocular, retroperitoneal, intraarticular or pericardial bleeding or intramuscular with compartment syndrome)
 - Extracranial bleeding-related hospitalizations (including trauma-related)
- Composite of any major bleeding or clinically-relevant non-major bleeding-related hospitalization (per the ISTH criteria [9, 10] for identification of bleeding-associated hospitalizations) at 6 and 12-months
- Intracranial hemorrhage (ICH), critical organ bleeding and extracranial bleeding-related hospitalizations as separate outcomes
- All-cause mortality at 6- and 12-months
- Incidence rates of recurrent VTE, any clinically-relevant bleeding-related hospitalization and all cause-mortality in rivaroxaban, DOAC and LMWH patients experiencing CAT regardless of the bleeding risk associated with cancer type
- Duration of anticoagulation treatment and rivaroxaban, DOAC and LMWH discontinuation rates at 3-, 6-, 12-months and all available follow-up

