9.5 Study size

Based on an incidence rate of VTE of 131.5 per 100,000 person-years and assuming that 18.6% of VTEs are associated with active cancer (1) and that 50% of patients with CAT have a recording for DOACs or LMWH within 30 days after initial VTE, we expect our cohort to include approximately 5,600 patients with CAT. Assuming a mean follow-up of 0.6 years following first CAT (according to the high mortality risk in these patients and the restriction to the first year following CAT) and incidence rates of 11.8 VTE recurrences, 14.4 significant bleeds and 80.0 deaths from any cause per 100 person-years, we expect to identify approximately 390 VTE recurrences, 480 significant bleeds and 2670 deaths from any cause within the first year after CAT. Based on the matching related fixed proportion of DOAC to LMWH users in our study cohort and the numbers mentioned above, this study would detect a significant difference between DOAC and LMWH users with 5% significance level and a power of 80% if the estimated HR is lower than 0.75, 0.77 or 0.89 respectively for VTE recurrence, serious bleeding or death from any cause. This is consistent with the HR of recurrent VTE ≤ 0.43 (supported by SELECT-D [14] and Costa et al. [15]) or with a more conservative HR (HR=0.71) as seen in the Hokusai VTE cancer trial for edoxaban (DOAC) compared to dalteparin (LMWH) [16].

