Cox proportional hazards regression is a method for investigating the effect of variables upon the time a specified event takes to happen. We will fit Cox proportional hazards regression models (with robust estimators) to compare event rates over time for the rivaroxaban (or any DOAC) and LMWH cohorts in the Xarelto SmPC and CAT guidance cancer type cohorts. As propensity score based methods will be assumed to

Reference Number: RD-SOP-1214
Supplement Version: 7

balance key characteristics of the treatment cohorts, the only independent variable that will be included into Cox regression model will be anticoagulant received (rivaroxaban or DOAC or LMWH). Results of Cox regression will be reported as hazard ratios (HRs) with 95% confidence intervals (CIs).

We will use an intention-to-treat approach to analyze the data in which, patients will be evaluated based on the initial anticoagulant prescription registered and will be followed until endpoint occurrence, end-of-database activity, end of data availability or end of designated follow-up time (3-, 6- or 12-months), whichever comes first. Time from treatment initiation to end of follow-up will then be considered the time at risk. On-treatment analysis (patients will be followed until endpoint occurrence, end-of-database activity, end of data availability, end of designated follow-up time (3-, 6- or 12-months), anticoagulant discontinuation or switch, whichever comes first) will be performed as a sensitivity analysis. No adjustments for multiple hypothesis testing will be performed.

Subgroup analyses

Analysis of the recurrent VTE, any clinically-relevant bleeding-related hospitalization and all-cause mortality outcomes among patients prescribed with rivaroxaban and any DOAC (apixaban, dabigatran, edoxaban, rivaroxaban) versus patients prescribed with LMWH patients for acute CAT will be performed stratifying by cancer subtypes (specific subtypes dependent on available sample sizes). To limit the number of analyses performed (and the impact of multiple hypothesis testing), subgroup analyses will only be performed on the primary effectiveness and safety endpoints (recurrent VTE, any clinically-relevant bleeding-related hospitalization and all-cause mortality).

Further descriptive analyses

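### Protocol 9.2.2 sets both no post-index minimum and a 3-month minimum of follow-up; applied patient by patient, the minimum would leave 3-month mortality, a primary outcome, without events

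*Protocol*

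**What the plan says.** Section 9.2.2 lists the time-frame rules as bullets. On eligibility after the index date: "There will be no minimum post-index eligibility requirement for patient identification". On the follow-up period, in the next bullet: "There will be a minimum of 3 months and maximum 12-months follow-up period". That bullet continues: "Patients will be followed from the first recording of AC use (7-30 days after CAT event) until the end of eligibility". Nothing says whether the 3 months is observed or potential follow-up, or how a patient who dies earlier is to be treated.

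Section 9.3.2 lists three primary outcomes, all at 3 months: recurrent VTE, the bleeding composite, and "All-cause mortality at 3-months". Section 8.1 states that recurrent VTE includes fatal events.

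Section 9.7 gives the main analysis rule. Patients are "followed until endpoint occurrence, end-of-database activity, end of data availability or end of designated follow-up time (3-, 6- or 12-months), whichever comes first". It sets no minimum.

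On the time origin, 9.2.2 defines the index date as the first recorded prescription, 7 to 30 days after the VTE. Section 9.1 places that prescription 7 to 30 days after the index date, so there the index date is the VTE. Section 9.3.2 has the secondary outcome "Recurrent VTE at 6- and 12-months post-index VTE", with the same anchor on one bullet for the bleeding composite. Section 9.7 says: "Time from treatment initiation to end of follow-up will then be considered the time at risk".

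**The concern.** A patient who dies or deregisters on day 40 after the index prescription satisfies the first bullet and fails the second. Whoever programs the cohort must choose between them, and the choice decides who enters the primary analysis.

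If the minimum is read as a condition on each patient, the cohort is selected on surviving the whole primary risk window. Three-month mortality could then have no events in either arm, so no hazard ratio could be estimated. Recurrent VTE and bleeding at 3 months would be estimated in survivors only, without fatal recurrences and fatal bleeds. The 6- and 12-month analyses would contain 3 months of follow-up in which nobody can die. If early mortality differs between the arms, so does the selection.

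The time origin is a smaller matter in the same rules. Two secondary outcomes count their horizon from the VTE, while time at risk is counted from the prescription.

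**Working it through.** **Inputs, all from protocol section 9.5 unless stated**
- Cohort: 5,600 ("we expect our cohort to include approximately 5,600 patients with CAT").
- Mean follow-up: 0.6 years.
- Rates per 100 person-years: 11.8 VTE recurrences, 14.4 significant bleeds, 80.0 deaths.
- Stated first-year events: about 390, 480 and 2,670.
- Gap from VTE to index prescription: 7 to 30 days (9.2.2).

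**Step 1: reproduce the plan's event counts.** Events = N × mean follow-up × rate.
- Deaths: 5,600 × 0.6 × 0.800 = 2,688 (stated 2,670).
- VTE: 5,600 × 0.6 × 0.118 = 396 (stated 390).
- Bleeds: 5,600 × 0.6 × 0.144 = 484 (stated 480).

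All agree within 3%. The study size therefore counts deaths over the whole first year, and it gives the high mortality as one reason for the short mean follow-up. It is built on a cohort that keeps early deaths.

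**Step 2: deaths that a patient-level minimum would remove.** Assuming a constant hazard λ, the 3-month risk is 1 − exp(−λ × 0.25). Only the 80 comes from the protocol; the other rates are assumptions that show the range.

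| Deaths per 100 person-years | 3-month risk | Deaths among 5,600 |
|---|---|---|
| 50 (assumed) | 11.8% | about 660 |
| 80 (protocol) | 18.1% | about 1,015 |
| 120 (assumed) | 25.9% | about 1,450 |
| 160 (assumed) | 33.0% | about 1,850 |

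With a constant hazard of 0.80 and death as the only exit, mean first-year follow-up is (1 − exp(−0.80))/0.80 = 0.69 years. The stated 0.6 is shorter, which fits additional censoring or a hazard that is higher early on. A higher early hazard would push the 3-month figure above 18%.

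**Step 3: consequence.** A patient who dies before 3 months cannot have 3 months of observed follow-up. Under a patient-level minimum, deaths within 3 months are 0 by construction, whatever the rate. At the protocol's rate, about 5,600 − 1,015 = 4,585 three-month survivors would remain for the 6- and 12-month analyses, before any loss through deregistration.

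**Step 4: the time origin.** If a horizon runs from the VTE but observation starts 7 to 30 days later, the observed share is:
- 6 months (182.5 days): 152.5/182.5 = 84% to 175.5/182.5 = 96%.
- 12 months (365 days): 335/365 = 92% to 358/365 = 98%.

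No such figure applies to the 3-month primary outcomes, because 9.3.2 states no VTE origin for them.

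**The case against.** The strongest reply is that no sentence excludes anyone for short follow-up. The selection criteria in 9.2.3 contain no post-index survival or follow-up condition. The only sentence about selection after the index date is the one setting no minimum. Section 9.7 ends follow-up at the earliest of several events and sets no floor. Section 9.5 counts first-year deaths. On this view, 3 and 12 months are simply the shortest and longest analysis horizons. Figure 1, which was not available for this review, may show the same. An empty primary outcome would also be noticed at once.

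Most of this stands. A reader might infer that early deaths will be dropped, but the documents do not support that: the selection, sizing and analysis sections point the other way. What remains is the wording. If 3 months is only the shortest horizon, then calling it a minimum is wrong, because 9.7 lets follow-up end sooner. If it means potential follow-up up to the end of data, it conflicts with patient identification that runs to the latest available data. No reading of the bullet is consistent with the rest of the protocol.

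A reader might also infer that the time-origin conflict shortens every horizon, including the primary 3 months. It does not go that far. The VTE anchor stands on two secondary bullets only, and mortality at 6 and 12 months does not carry it.

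**Conclusion.** Section 9.2.2 contains an unresolved contradiction that must be corrected before the cohort is built. It is a defect of wording, not evidence that early deaths will be excluded. It matters because one literal reading makes one of three primary outcomes impossible to estimate and removes fatal events from the other two.

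Under that reading, about 18% of patients would be lost, or roughly 1,015 of 5,600. This rests on a constant hazard at the protocol's first-year death rate; assumed early rates of 50 to 160 per 100 person-years give about 12% to 33%. The 5,600 covers all CAT patients with a DOAC or LMWH record, so counts in the restricted cancer-type cohorts would be smaller. That 3-month deaths would be zero needs no assumption about the rate.

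The time-origin conflict is real but secondary. It leaves about 84% to 96% of the 6-month window and 92% to 98% of the 12-month window for two secondary outcomes.

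**What to change.** 1. In 9.2.2, delete the 3-month minimum. State that follow-up starts at the index prescription, has no minimum, and ends at the event, death, deregistration, end of data, or 3, 6 or 12 months after the index date, whichever is first. State that death never counts as insufficient follow-up.

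2. If a minimum is wanted, define it only as potential follow-up: an index date at least 3 months before the last linked-data date, never observed survival. This costs the patients indexed in the last 3 months. With January 2013 to March 2019 as 75 months and even accrual assumed, that is about 3/75 = 4% of the cohort. The identification period, which now runs to the latest available data, must be changed to match.

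3. Use one time origin. Bring the meaning of index date in 9.1 into line with 9.2.2, and count the 6- and 12-month outcomes in 9.3.2 from the index prescription, as 9.7 does.

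Items 1 and 3 change wording only and cost no data. Item 2 is optional and carries the cost given above.

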9.2.3 Selection criteria

To be included in the study patients will have to:

- Be ≥ 18 years of age at the time of anticoagulation initiation
- Have active cancer and acute DVT and/or PE
- Treated with rivaroxaban (or any DOAC) or LMWH as their first recorded anticoagulant prescription 7 to 30 days post-acute CAT event diagnosis
- Have been active in the data set for at least 12-months prior to the index event and had at least one provider visit in the 12-months prior to the acute VTE event

We will exclude patients with:

- Evidence of atrial fibrillation, recent hip/knee replacement (with 90 days of CAT), ongoing VTE treatment, valvular heart disease defined as any rheumatic heart disease, mitral stenosis or mitral valve repair/replacement
- History of inferior vena cava filter before cohort entry
- VKA use between cohort entry and index day (initiation of DOAC or LMWH)
- Evidence of any type of therapeutic anticoagulation use during all available look-back period per written prescription or patient self-report
- Initiation of rivaroxaban or other DOACs or LMWH during the study period at non-therapeutic doses (e.g., enoxaparin at a dose other than 1 mg/kg twice daily or 1.5 mg/kg once daily; dalteparin at a dose other than 200 IU/kg of total body weight)
- Pregnancy
- Recording indicative of palliative care before cohort entry
- Any clinically-relevant bleeding-related hospitalization or VTE recurrence between the initial CAT and the start of observation

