9.1 Study design

[figure not shown]
We will perform a retrospective cohort analysis using CPRD GOLD and Aurum HES-linked datasets, from January 2013 through latest available data. Patient identification and flow is depicted in **Figure 1**.

Adults diagnosed with active (primary or metastatic) cancer experiencing a hospitalization or emergency department admission or a primary care visit with an incident VTE, being administered rivaroxaban or other DOACs or a LMWH will be included. CPRD and their linked databases do not include information on in-hospital medication use. Patient discharge with anticoagulation supply is routine practice. However, neither the type of AC use, the date of medication start nor the amount of supply are recorded in CPRD or linked databases. Therefore, the first AC recording by the GP, between day 7 and day 30 after index date, will be used to define the type and duration of AC use and to allocate patients with acute VTE to the respective exposure, i.e. DOAC or LMWH. The 7-30 days window has been selected based on previous studies in this population [2, 4]. Subjects will need to be registered with their primary care practitioner (PCP) for at least 12-months prior to the acute CAT event.

Active cancer in this study will be defined as cancer being actively treated, diagnosed within 6-months prior of the index CAT or associated with metastatic disease (regardless of time from initial cancer diagnosis). We will exclude patients with an indication for OAC use to treat other conditions (i.e. atrial fibrillation, prophylaxis after hip/knee replacement in the last three months, stable coronary or peripheral artery disease, long-term VTE prophylaxis) or use of OAC during the 12-months prior to the CAT.

Figure 1: Schematic of VTE analysis

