9.2.1 Study population

The study population of interest will be adults diagnosed with active (primary or metastatic) cancer experiencing a hospitalization or emergency department admission or a primary care visit with an incident VTE, being administered rivaroxaban or other DOACs or a LMWH on or after January 1, 2013. We will identify the first record of anticoagulant therapy between day 7 and day 30 following CAT diagnosis. Subjects will need to be registered with their PCP for at least 12-months prior to the acute CAT event. Patients with cancer diagnoses and/or cancer-specific therapies including chemotherapy, radiotherapy, hormonal therapy and immunotherapy will be identified. Active cancer will be assumed to last 180 days following a cancer diagnosis or therapy recording. Active cancer episodes will be extended for 180 days from the day of the subsequent cancer-specific recording if it is recorded within the initial active cancer episode. Metastatic cancers will assumed to be active ever since first recording.

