9.3.3 Covariate definition

Patient baseline characteristics such as age, gender, comorbidities, cancer-specific data and comedications will be collected at the index date or from the last recorded value within the baseline period. The presence of characteristics will be assessed from patients' medical and pharmacy data in the baseline period (see Annex 1).

Demographic characteristics

- Sex
- Age
- Race
- Individual DOAC or LMWH used to treat CAT
- Number of days between CAT and first recording of anticoagulation use

Clinical characteristics

- Presence of the following clinical characteristics will be assessed from patients' medical and pharmacy data in the baseline period:
 - **Comorbidities/prior history/risk scores:**
 - Number of days from January 1, 2013 to qualifying CAT diagnosis
 - Cancer type(s) present at CAT diagnosis
 - Metastatic disease at time of CAT diagnosis
 - Active/recent treatment (within 3-months pre- or post-CAT diagnosis)
 - Chemotherapy/immunotherapy
 - Radiation therapy
 - Surgical
 - Initial anticoagulation therapy on day of CAT diagnosis
 - Intracranial bleeding
 - Systemic embolism
 - Deep vein thrombosis
 - Pulmonary embolism
 - Heart failure
 - Hypertension
 - Ischemic stroke/transient ischemic attack
 - Peripheral vascular disease
 - Myocardial infarction
 - Percutaneous coronary intervention
 - Coronary artery bypass grafting
 - Any major bleed

- Major adverse limb events (need for surgical or endovascular revascularization or limb amputation)
- Gastrointestinal bleeding
- Central venous catheter
- Liver disease
- Coagulopathy
- Gastroesophageal reflux disease/heartburn
- Anemia
- Asthma
- Chronic obstructive pulmonary disease
- Sleep apnea
- Smoker
- Alcohol abuse
- Anxiety
- Depression
- Lower extremity paralysis
- Psychosis
- Osteoarthritis
- Diverticulitis
- Crohn's disease or ulcerative colitis
- Active or treated *Helicobacter pylori*
- Hypothyroidism
- Recent major surgery within 12 weeks of index event
- Dementia
- Recent trauma (with 90-days)

- Primary hypercoagulable state (e.g., activated protein C resistance, prothrombin gene mutation, antiphospholipid syndrome, lupus anticoagulant syndrome and other primary thrombophilia (per Read code; ICD-9 or -10 coding provided in Annex 1))
- Prior history of VTE
- Varicose veins
- Chronic venous insufficiency (per Read code or ICD-9 /-10 coding provided in Annex 1)
- Acute coronary syndrome
- Carotid stenosis
- Pneumonia
- Osteoporosis
- Orthopedic surgery

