- 1.- HES Admitted Patient Care (HES APC) : Complete hospital episode information (admission and discharge dates, diagnoses (identifying primary diagnosis), specialists seen under and procedures undertaken) for each linked patient with a hospitalization record. This is necessary if we do not want to miss any study hospitalized outcome.
- 2.- HES Accident and Emergency (HES A&E) data of patients attending hospitals that may be further be hospitalized. From all information recorded we are specially interest in: A&E diagnosis.
- 3.- Death Registration data contains data from the Office for National Statistics (ONS) and includes information on the official date and causes of death (using ICD codes). This is important to ascertain potential outcomes that may not be in previous sources, but can identify patients dying from the outcome we are studying.

We will request approval to obtain the three linked data sources (HES APC, HES A&E, ONS Death registration) to ascertain all potential study outcome of interest resulting in a hospitalization or being the cause of death. On the other hand we will not request The HES Outpatient (HES OP), as data completeness is an issue in some OP fields and outpatient information may not add relevant clinical information of use for our outcome definitions.

Patients registered in CPRD database are age, sex, and geographically representative of the UK population, and has been extensively validated for use in epidemiological studies [5]. Updated, valid, linked data are available through the CPRD Division of the UK Medicines and Health Care Products Regulatory Agency

Research at the CPRD requires approval from the CPRD Independent Scientific Advisory Committee (ISAC).

The Read classification is used to code specific diagnoses [11, 12] and a drug dictionary based on data from the Gemscript classification is used to record prescriptions [13]. Currently, active patients included in CPRD-GOLD are over 3 million and the corresponding number in Aurum approximates 13 million.

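### The day 7-30 window counts from the CAT, so unequal discharge supply between DOACs and LMWH would give the arms different index hospital stays, which the plan neither measures nor adjusts for

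*Protocol*

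**What the plan says.** - Entry (9.2.3): "Treated with rivaroxaban (or any DOAC) or LMWH as their first recorded anticoagulant prescription 7 to 30 days post-acute CAT event diagnosis". Section 9.2.1 has the same origin: "We will identify the first record of anticoagulant therapy between day 7 and day 30 following CAT diagnosis". Sections 9.2.2 and 9.3.1 also count from the CAT; section 9.1 once counts from the index date.
- Hospital treatment (9.1): "CPRD and their linked databases do not include information on in-hospital medication use"; "Patient discharge with anticoagulation supply is routine practice"; yet "neither the type of AC use, the date of medication start nor the amount of supply are recorded in CPRD or linked databases".
- Setting (9.2.2): "Cohort entry: CAT diagnosis, hospitalization or emergency department admission or primary care visit with an incident VTE event". So some patients have an inpatient stay and some do not.
- Covariates (9.3.3): the list has "Number of days between CAT and first recording of anticoagulation use" and a count of baseline hospitalizations. It does not have the length of the CAT admission.
- Data (9.4): HES APC will be requested, with "Complete hospital episode information (admission and discharge dates" and more, so the stay can be measured.
- Analysis (9.7): overlap weights from a logistic propensity score balance the modelled covariate means exactly. The Cox model contains treatment only.
- Limitations (9.9): missed in-hospital starts are treated as non-differential misclassification that biases towards the null. Stay and supply are not mentioned.

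**The concern.** The interval from CAT to first GP record is, for an admitted patient, the sum of two parts: time in hospital and days covered by the discharge supply. Eligibility depends on the sum, and the propensity score can see only the sum. If one drug is usually discharged with a longer supply, its users reach day 30 after a shorter stay, so that arm loses more of its long-stay patients. Weighting then compares patients with the same sum, and at the same sum the drug with the shorter supply has the longer stay.

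A long CAT admission plausibly marks a sicker patient with a higher risk of death and bleeding, two of the three primary outcomes. A stay difference produced by the entry rule and the weighting could therefore appear as a drug effect. None of the planned sensitivity analyses adjusts for stay or moves the window. Matching uses the same score, the on-treatment analysis keeps the same cohort, and the analysis restricted to hospital or emergency department admissions keeps the affected patients.

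**Working it through.** The protocol gives no figure of its own on this point.

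**Inputs from the protocol:** window 7 to 30 days from the CAT; supply routine and unrecorded; interval listed as a covariate, stay not listed; exact mean balance of modelled covariates; treatment-only Cox model.

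**Assumptions, not in the protocol:** stay log-normal with median 6 days and sigma 0.9; supply a mix of 7, 14, 21 and 28 days; GP record 0 to 5 days before the supply ends; hazard 2%, 3% or 5% higher per hospital day; no drug effect; same stay distribution in both arms before selection.

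**Step 1, the window.** Interval T ≈ stay + supply, kept if 7 ≤ T ≤ 30. Ignoring early renewal, the longest stay that qualifies is 30 − supply: 30 − 14 = 16 days with a 14-day supply, 30 − 28 = 2 days with a 28-day supply.

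**Step 2, the balancing.** If weighting makes mean T equal in the two arms, then

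difference in mean stay = −(difference in mean supply),

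both taken in the weighted sample. This is algebra and does not depend on the stay distribution. A separate simulation with gamma-distributed stays (mean about 6 days), all patients admitted and supply means of 14 vs 10 days confirms it. The stay difference is about −0.5 days before weighting. After balancing T, stay is 4.98 vs 7.89 days (−2.91) and the supply difference is +2.91.

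**Step 3, size with supply mixes, all patients admitted** (DOAC first; means 19.6 vs 14.7 days):

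| Quantity | DOAC | LMWH |
|---|---|---|
| Share entering the cohort | 70% | 79% |
| Mean stay before weighting, days | 5.7 | 6.6 |
| Mean stay after balancing T, days | 5.4 | 7.1 |

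To first order HR ≈ exp(slope × stay difference), with a difference of 5.4 − 7.1 = −1.7 days:
- 2% per day: exp(−0.02 × 1.7) = 0.97; simulated 0.97
- 3% per day: exp(−0.03 × 1.7) = 0.95; simulated 0.95
- 5% per day: exp(−0.05 × 1.7) = 0.92; simulated 0.91

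With closer supply means (18.6 vs 16.1 days) the simulated HRs are 0.98, 0.98 and 0.96. With equal supply the HR is 1.00. If LMWH has the longer supply the HR lies above 1.

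**Step 4, patients who are not admitted** (3% per day, means 19.6 vs 14.7). If their record day is unrelated to supply, the HR is about 0.96 with 70% admitted and 0.97 to 0.98 with 40% admitted. If they go home with the same drug-specific supply, there is little dilution and the HR stays at 0.94 to 0.95. Overall range: about 0.94 to 0.98.

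**Step 5, other covariates.** In the gamma simulation (14 vs 10 days), a scored covariate correlated 0.5 with stay reduces the weighted stay difference from 2.89 to 2.70 days with all admitted, and from 1.02 to 0.84 days with 70% admitted. It helps only in part.

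**Step 6, stay added to the score.** The weighted stay difference is 0.0 days and the HR returns to 1.00 in the supply-mix scenarios. In the gamma runs that include non-admitted patients the HR is 0.995 to 1.00.

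**The case against.** The strongest objection is that the premise is not in the documents. Section 9.1 says that supply is routine and unrecorded; nowhere does the protocol say that it differs by drug. A reader might infer that the mortality comparison is biased, and biased in favour of DOACs. The documents support neither: with equal supply there is no effect, and the sign depends on which drug has the longer supply. The hazard slope per hospital day is assumed too.

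A reader might also set the spurious HR beside the mortality HR of 0.89 that section 9.5 calls detectable. That benchmark rests on about 2,670 deaths in the first year (5,600 × 0.6 × 0.80 = 2,688), whereas the primary outcome is mortality at 3 months, so the comparison is not valid. Much larger distortions can be produced by giving every patient on a drug one fixed supply, but that is artificial. In that case interval minus stay also separates the arms completely, so the covariate fix would not repair it.

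Three further points stand in part:
- The score also holds metastatic disease, cancer type, surgery, frailty and laboratory values. Some of these plausibly track stay, and they would reduce the effect.
- The interval is listed under demographics, beside the individual drug used, which cannot be in the score. Section 9.7 names demographics among the score variables but promises all listed items only for clinical characteristics. If the interval were left out, the window effect alone would remain: 5.7 vs 6.6 days, or exp(−0.03 × 0.9) = 0.97.
- The window follows previous studies and a harmonised programme, and section 9.9 admits that in-hospital starts are missed. It does not cover this mechanism, which would be differential and could act in either direction.

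**Conclusion.** The point holds as a conditional weakness. The entry rule and the listed covariates leave the comparison open to a difference in index length of stay whenever usual discharge supply differs between DOACs and LMWH, and balancing the interval enlarges that difference. Under the assumed supply means of 19.6 vs 14.7 days and 3% per hospital day, the spurious mortality HR is about 0.94 to 0.98 before allowing for other covariates. It is 1.00 with equal supply and above 1 if LMWH supply is longer. The documents do not establish that such a bias exists, its direction, or that it is large enough to produce a false positive. What they do establish is that supply is unrecorded, so equality between the drugs cannot be checked directly, and that the stay, which can be measured, is not used.

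**What to change.** In section 9.3.3, add the length of the CAT admission (HES APC admission to discharge; 0 if not admitted) and an admitted yes/no indicator, and include both in the propensity score. In section 9.7, report weighted mean stay and the discharge-to-first-record gap by arm; the gap is the nearest observable stand-in for supply.

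Stay and interval together nearly reveal supply, so also report overlap and effective sample size. If separation appears, use stay without the interval. Effective sample size in the simulated supply mixes was roughly 89% to 99%. In one run it was 93% with the interval alone, 89% with interval and stay, and 99% with stay alone.

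A sensitivity analysis that counts the window from discharge for admitted patients is optional. In it, long-stay patients would start follow-up later after the CAT.

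The cost is two covariates from data already requested, two extra lines in the balance table and a small loss of precision.
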